4.1. Background

Rheumatoid Arthritis (RA) is a systemic, chronic, autoimmune and inflammatory disease that affects joints, muscles, tendons, connective tissues and fibrous tissues^{1,2}. RA is considered to be the most common autoimmune disease in adults that affects approximately 1% of the global population^{3,4}.

In The Global Burden of Disease 2010 study "GBD 2010 Study" which was conducted in 187 countries, it was found that Disability-Adjusted Life Year (DALY "per 100000") for RA in 1990 was 63 which was increased in 2010 to be 70⁵.

Data from a systematic literature review of Medline, Embase and Global Health Library which reclaimed a total of 335 publications showed that in 1990, the estimated crude prevalence of RA in Africa based on the available studies was 0.36% (2.3 million affected individuals) which was thought to be increased in 2010 to 0.42% with burden of 4.3 million affected individuals⁶.

During the past 30 years, the management of RA has changed drastically as few therapeutic agents were extant⁷. At the present time, numerous therapeutic agents are used in managing RA along with relieving signs and symptoms such as DMARDs, Glucocorticoids and NSAIDs^{7,8}.

In 2016, Despite the fact that The European League Against Rheumatism (EULAR) recommended that Methotrexate (MTX) should be part of the first line treatment strategy, Leflunomide or Sulfasalazine were recommended as part of the first treatment strategy in patients with a contraindication to Methotrexate or with early intolerance⁸.

Leflunomide is one of the most used DMARDs around the world, it can be used as a monotherapy or in combination with other DMARDs to inhibit the production of inflammatory cells and accordingly to reduce inflammation⁹.

In a number of studies which were conducted to investigate the efficacy and safety of Leflunomide n RA management, it was found that Leflunomide was equivalent to Methotrexate and its safety profile was acceptable compared to other DMARDs^{9,10,11}. It was also found that Leflunomide was superior to Methotrexate in terms of Quality of Life measurements^{9,10,11}.

4.2. Rationale

The aim of this study is to assess the clinical efficacy and safety of Leflunomide as first line therapy and as add-on therapy to other DMARDs (such as Methotrexate, Hydroxychloroquine, Sulfasalazine) with or without Steroids in Egyptian patients with Active Rheumatoid Arthritis.

4.3. Incidence and Prevalence

RA is considered to be the most common autoimmune disease in adults that affects approximately 1% of the global population^{3,4}.

In The Global Burden of Disease 2010 study "GBD 2010 Study" which was conducted in 187 countries, it was found that Disability-Adjusted Life Year (DALY "per 100000) for RA in 1990 was 63 which was increased in 2010 to be 70⁵.

Data from a systematic literature review of Medline, Embase and Global Health Library which reclaimed a total of 335 publications showed that in 1990, the estimated crude prevalence of RA in Africa based on the available studies was 0.36% (2.3 million affected individuals) which was thought to be increased in 2010 to 0.42% with burden of 4.3 million affected individuals⁶.

In 2004, A study was conducted to assess the prevalence of rheumatic diseases in rural Egypt and the results showed that in 857 individuals, The prevalence of RA in rural Egypt was 0.29% in the population, which was similar to other oriental rural populations but lower than Western populations¹².

5. Study Questions and Objectives

5.1. Study Questions

- 1. What is the clinical efficacy of Leflunomide as first line therapy and as add-on therapy to other DMARDs (such as Methotrexate, Hydroxychloroquine, and Sulfasalazine) with or without Steroids use in Egyptian patients with Active Rheumatoid Arthritis ?
- 2. What are the pattern of management and characteristics of Egyptian patients with Active Rheumatoid Arthritis receiving Leflunomide treatment?
- 3. What is the clinical safety of Leflunomide as first line therapy and as add-on therapy to other DMARDs (such as Methotrexate, Hydroxychloroquine, and Sulfasalazine) with or without Steroids use in Egyptian patients with Active Rheumatoid Arthritis?

5.2. Primary Objectives

 Assessing the clinical efficacy of Leflunomide as first line therapy and as add-on therapy to other DMARDs (such as Methotrexate, Hydroxychloroquine, Sulfasalazine) with or without Steroids in Egyptian patients with Active Rheumatoid Arthritis.

5.3. Secondary Objectives

1. Describing pattern of management and characteristics of Egyptian patients with Active Rheumatoid Arthritis receiving Leflunomide treatment.

 Identifying the safety profile of Leflunomide whether used as first line therapy and/or as add-on therapy to other DMARDs (such as Methotrexate, Hydroxychloroquine, Sulfasalazine) with or without Steroids in Egyptian patients with Active Rheumatoid Arthritis.

6. Study Methods

6.1. Study Design

This is a phase IV, multi-centric, prospective, observational study to assess the clinical efficacy and safety of Leflunomide as first line therapy and as add-on therapy to other DMARDs (such as Methotrexate, Hydroxychloroquine, Sulfasalazine) with or without Steroids use in Egyptian patients with Active Rheumatoid Arthritis.

6.2. Study Flowchart and Graphical Study Design

CLEAR Study Flowchart

6.3. Recruitment Modalities

6.3.1.Selection of Subjects

6.3.1.1. Inclusion Criteria Patient must meet ALL of the following criteria to be eligible for enrolment into the study

- 1. Active Rheumatoid Arthritis patients selected according to the ACR/EULAR classification 2010 criteria with score ≥ 6 points.
- 2. Male or female patients aged 18-60 years old.
- 3. Leflunomide naïve patients or patients with previous Leflunomide administration (after at least 6 month wash out period from date of baseline visit) who will be prescribed Leflunomide at the sole decision of the treating physician.

Study Protocol: EVA_CLEAR_11022017 Version Number: Final V2.0/19-Jun-2017

- Patients with or without another DMARDs including Methotrexate, Sulfasalazine and/or Hydroxychloroquine with or without steroids use who experienced therapy resistance, inadequate response or intolerance.
- 5. Patients read, understand and signed informed consent prior to inclusion.
- 6. Patients willing to complete and literate in the language of the available Health Assessment Questionnaire (HAQ Disability Index) either alone or with minimal assistance from caregivers and/or trained site personnel.

6.3.1.2. Exclusion Criteria Patient meeting the following criteria is not eligible for enrolment into the study

- 1. Female patients who are pregnant or lactating at the time of inclusion or those who are planning for pregnancy within the coming year from the time of inclusion to the study.
- 2. Patients with contraindications to active constituent of Leflunomide.
- 3. Patients with severe concurrent infection (necessitating IV antibiotics or hospitalization).
- 4. Patients with history of non-treated hepatitis B &/or C infection.
- 5. Patients with history of severe liver disease (child C class).
- 6. Patients with history of severe renal insufficiency (creatinine clearance ≤30 ml/min.).

6.3.2. Selection of Investigators

The study will be conducted by rheumatologists.

In order to ensure the representativeness of investigators, the participating investigators will be randomly selected among an extended list of sites (private clinics; rheumatologist) provided by the study sponsor.

6.4. Duration of Study Participation

3 months for recruitment and 9 months for treatment.

7. Management of Data

7.1. Source Data

Source documents are original documents, data, and records from which participants' CRF data are obtained. These include, but are not limited to, hospital records (from which medical history and previous and concurrent medication may be summarized into the CRF), clinical and office charts, laboratory and pharmacy records...etc.

CRF entries will be considered source data if the CRF is the site of the original recording (e.g.: there is no other written or electronic record of data)

All documents will be stored safely in confidential conditions. On all study-specific documents,

Study Protocol: EVA_CLEAR_11022017 Ve

other than the signed consent, the participant will be referred to by the study participant number/code, not by name.

Direct access to source documents will be granted to DATACLin CRO monitoring team as authorized representatives from the sponsor and to regulatory authorities to permit trial-related monitoring, audits and inspections.

7.2. Data Collection

	Data Collection Schedule					
Data to be collected	Visit 1 (Baseline)	Visit 2 (Week 6)	Visit 3 (Week 12)	Visit 4 (Week 20)	Visit 5 (Week 28)	Visit 6 (Week 36)
Informed consent	Х					
Inclusion/ Exclusion	Х					
Physical Examination/ Vital Signs ¹	х	х	х	х	х	х
Demographics	Х					
Smoking Status	Х					
Alcohol Consumption	Х					
Medical history	Х					
Gynecological History (FEMALES ONLY)	х					
Concomitant Medications	х	х	x	x	х	х
RA History ²	Х					
Disease Assessment ³	Х	Х	Х	Х	Х	х
Laboratory Tests ⁴	Х	Х	Х	Х	Х	Х
Health Assessment Questionnaire (HAQ Disability Index) ⁵	x	х	x	x	х	x
Poor Prognostic Factors ⁶	х					
Adverse Events & Serious Adverse Events		Х	Х	х	Х	Х
Study Completion Form						X
1: Physical Examination/Vitals S	ians: Heiaht will be	collected in V1 c	only			

7.2.1.Data Collection Schedule

2: Rheumatoid Arthritis History will include RA Duration, Previous/Current therapies including duration, dose, adverse events/serious adverse events experienced during previous treatment and Reason for starting Leflunomide* (previous DMARDs failure, insufficient response, allergy, intolerance, side effects) *dose (if the patient received loading dose or not) and Previous X-RAY reports.

3: Disease Assessment will be done by Clinical Disease Activity Index (CDAI).

4: Laboratory Tests include CBC, ESR assessed by Westergren method (First hour), C-reactive protein (titer), AST, ALT, Sr Cr, Sr ACPA, Sr RF titer, FBG, HBsAg and HCV-Ab.

Study Protocol: EVA_CLEAR_11022017

5: Stanford University-Health Assessment Questionnaire (HAQ Disability Index).
 6: Poor prognostic factors: Presence of 1 or more of; Bony erosions by radiograph, High swollen joint count, Extra-articular disease (nodules, vasculitis, Felty's syndrome), Functional limitation (HAQ), High disease activity as measured by composite indices (DAS28, SDAI and/or CDAI), High acute phase reactants (CRP and ESR) or High RF and/or anti-CCP.

7.2.2. Data Collection Process

Data will be collected using NCR CRF according to the below manner;

At Baseline Visit:

Data on Informed consent, Inclusion and exclusion criteria, Demographics, Smoking status, Alcohol consumption, Medical history, Gynecological History for female patients only, Concomitant medications, Laboratory tests and Poor prognostic factors will be collected along with RA history.

Disease assessment (CDAI) and Physical examination will be done and also Vital signs will be recorded.

Patients will fill Health Assessment Questionnaire (HAQ Disability Index) and related data will be recorded.

At Visit 2 (Week 6 ± 2 weeks) & Visit 3 (Week 12 ± 2 weeks) & Visit 4 (Week 20 ± 2 weeks) & Visit 5 (Week 28 ± 2 weeks):

Data on Concomitant medications and Laboratory tests will be collected.

Disease assessment (CDAI) and Physical examination will be done and also Vital signs will be recorded.

Patients will fill Health Assessment Questionnaire (HAQ Disability Index) and related data will be recorded.

Data on Adverse events/Serious adverse events experienced by patient since the previous visit will be documented.

At Visit 6 (Week 36 ± 2 weeks):

Data on Concomitant medications and Laboratory tests will be collected.

Disease assessment (CDAI) and Physical examination will be done and also Vital signs will be recorded.

Patients will fill Health Assessment Questionnaire (HAQ Disability Index) and related data will be recorded.

Data on Adverse events/Serious adverse events experienced by patient since the previous visit will be documented.

Study Completion Form will be also filled.

Data on Adverse events/Serious adverse events experienced by patient since the previous visit will be documented.

Study Completion Form will be also filled.

7.3. Conventions (Data Entry)

Double data entry (interactive verification): Two people independently enter the same data and the second entry operator resolves discrepancies between first and second entry while being aware of the values entered by the first entry operator.

Data entry will be done using ClinCapture version 2.1.15.9.

7.4. Data Validation and Discrepancy Management by the CRO

The computerized handling of data by DATACLin CRO may generate additional queries automatically through pre-programmed and tested validation rules. Validation rules will be detailed in the Data validation Plan (DVP).

In addition to automatic validation rules, manual/ medical review of data may generate further queries that will be raised on the system as well. Site staff will be responsible for resolving automatic and manual queries by confirming or modifying the data questioned.

7.5. Clinical Data Coding

DATACLin CRO will be responsible for coding of safety data using the latest available version of MedDRA (Medical Dictionary for Regulatory Activities).

Collected trade names of drugs (e.g. concomitant medications) will be also coded to the relevant generic names.

8. Statistical Considerations

8.1. Determination of Sample Size

The primary objective of CLEAR study is to assess the clinical efficacy of Leflunomide as first line therapy and as add-on therapy to other DMARDs (such as Methotrexate, Hydroxychloroquine, Sulfasalazine) with or without Steroids as measured by the mean relative change in Clinical Disease Activity Index (CDAI) and Health Assessment Questionnaire (HAQ Disability Index) among patients with active rheumatoid arthritis.

Considering an alpha error of **5%** using two-sided 95% CI of Wilcoxon signed-rank test and a study power of **80%**, a sample of **332 patients** will be required to detect an effect size of **0.158** between baseline and study endpoint, plus an expected **drop-out rate of 20%** during the 9 months observational study duration. Thus, a sample of **398 patients** will be appropriate that rounded to **400 patients**.

8.2. Randomization

Not Applicable.

8.3. Analysis Population

The obtained clinical data will be analyzed on an intention-to-treat basis. Primary analysis will be done by intention-to-treat including all eligible enrolled patients with at least one treatment dose and post first assessment score (CDAI and HAQ) attending any post treatment visit and efficacy variables will be analyzed using the last-observation-carried-forward convention (LOCF).

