MEDICINAL PRODUCT	Arthfree (Leflunomide 20mg) Dose: 1 tablet once daily, should be swallowed whole with sufficient amounts of liquids. The extent of Leflunomide absorption is not affected if taken with meals. Doses higher than 20 mg/day are not recommended. Improvement in the rheumatoid condition usually starts after 4 to 6 weeks and may further improve up to 4 to 6 months. Loading dose: a tablet of Leflunomide 100 mg for three days. should be swallowed whole with sufficient amounts of liquids. The extent of Leflunomide absorption is not affected if taken with meals. Due to the long half-life in patients with rheumatoid arthritis and recommended dosing interval (24 hours), a loading dose is needed to provide steady-state concentrations more rapidly. Patients will be prescribed Arthfree (Leflunomide) at the sole decision of the treating physician.					
	This phase IV study will last for 9 months in addition to recruitment period of 3 months. A total of 6 visits will be performed as shown in the table below;					
	Visit 1	Visit 2	Visit 3	Visit 4	Visit 5	Visit 6
DATA COLLECTION SCHEDULE	Baseline & ICF signing	Week 6 (± 2 weeks)	Week 12 (± 2 weeks)	Week 20 (± 2 weeks)	Week 28 (± 2 weeks)	Week 36 (± 2 weeks) EOS
	Clinical Assessment	Clinical Assessment	Clinical Assessment if applicable Clinica Assessm		Clinical Assessment	
	Lab Data	Lab Data Lab Data if applicable Lab		Lab Data		
	Safety Data					
DATA TO BE COLLECTED (FOR PRIMARY AND SECONDARY OBJECTIVES)**	 At Baseline Visit: Data on Informed consent, Inclusion and exclusion criteria, Demographics, Smoking status, Alcohol consumption, Medical history, Gynecological History for female patients only, Concomitant medications, Laboratory tests and Poor prognostic factors will be 					

	collected along with RA history.				
	Disease assessment (CDAI) and Physical examination will be done and also Vital signs will be recorded.				
	Patients will fill Health Assessment Questionnaire (HAQ Disability				
	Index) and related data will be recorded.				
	At Visit 2 (Week 6 ± 2 weeks) & Visit 3 (Week 12 ± 2 weeks) & Visit				
	4 (Week 20 ± 2 weeks) & Visit 5 (Week 28 ± 2 weeks):				
	Data on Concomitant medications and Laboratory tests will be collected.				
	Disease assessment (CDAI) and Physical examination will be done and also Vital signs will be recorded.				
	Patients will fill Health Assessment Questionnaire (HAQ Disability Index) and related data will be recorded.				

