STATISTICAL CONSIDERATIONS	 The primary objective of CLEAR study is to assess the clinical efficacy of Leflunomide as first line therapy and as add-on therapy to other DMARDs (such as Methotrexate, Hydroxychloroquine, Sulfasalazine) with or without Steroids as measured by the mean relative change in Clinical Disease Activity Index (CDAI) and Health Assessment Questionnaire (HAQ Disability Index) among patients with active rheumatoid arthritis. Considering an alpha error of 5% using two-sided 95% CI of Wilcoxon signed-rank test and a study power of 80%, a sample of 332 patients will be required to detect an effect size of 0.158 between baseline and study endpoint, plus an expected drop-out rate of 20% during the 9 months observational study duration. Thus, a sample of 398 patients will be appropriate that rounded to 400 patients. Randomization method 						
	Not applicable.						
	Statistical methodologies:						
	- Descriptive analysis:						
	 Percent (%) distribution for all categorical variables and 						

	mean with (SD) and median (Minimum: Maximum) for				
	- Comparative analysis:				
	 Student t-test and One Way ANOVA to estimate the comparison between the treatment arms for the numerical variables (according to their distribution; non-parametric substitution tests could be used). 				
	 Paired t-test and repeated measure ANOVA test to estimate the change in numerical variables throughout the study visits (according to their distribution; non-parametric substitution tests could be used). Chi2 test (or Fisher's Exact test) for unpaired and McNemar's test for paired categorical variables. 				
	All tests will be performed on the 5% level of significance.				
	 Any deviation(s) from the original statistical plan will be described in the final report). 				
	 Procedure for accounting for missing, unused, and spurious data will be explained in the statistical analysis plan (SAP). 				
	Interim analysis				
	When approximately the enrolled patients completed 50% of their visits (after Visit 3), an interim analysis for safety and efficacy will be conducted by an independent data monitoring committee. Serious adverse events will be monitored by the committee on an ongoing basis throughout the study.				
	- Protocol planned date: June 2017				
	- First patient In (FPI): September 2017				
	- Last patient In (LPI): December 2017				
ESTIMATED DURATION	- Last patient Out (LPO): September 2018				

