8.5.1. Efficacy Variables

- Clinical Disease Activity index (CDAI) in baseline and at week 36 to measure disease severity and relative mean change between study endpoints.
- Health assessment questionnaire (HAQ Disability Index) in baseline and at week 36 to measure relative mean change between study endpoints.

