8.7.2. Comparative Analysis

o Student t-test and One Way ANOVA to estimate the comparison between the treatment

Study Protocol: EVA_CLEAR_11022017 Version Number

arms for the numerical variables (according to their distribution; non-parametric substitution tests could be used).

- Paired t-test and repeated measure ANOVA test to estimate the change in numerical variables throughout the study visits (according to their distribution; non-parametric substitution tests could be used).
- Chi2 test (or Fisher's Exact test) for unpaired and McNemar's test for paired categorical variables.
- All tests will be performed on the 5% level of significance.
- Any deviation(s) from the original statistical plan will be described in the final report.

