8.8. Handling of Missing Values

- Procedure for accounting for missing, unused, and spurious data will be explained in the statistical analysis plan (SAP).

9. Treatment

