11.5. Discontinuation / Withdrawal of participants from study

Each participant has the right to withdraw from the study at any time. In addition, the investigator may discontinue a participant from the study at any time if the investigator considers it necessary for any reason including:

- 1. Ineligibility (either arising during the study or retrospective having been overlooked at screening)
- 2. Significant protocol deviation
- 3. Significant non-compliance with treatment regimen or study requirements
- 4. Disease progression which requires discontinuation of the study medication or results in inability to continue to comply with study procedures.
- 5. Consent withdrawn.
- 6. Lost to follow up

The reason for withdrawal will be recorded in the CRF.

If the participant is withdrawn due to an adverse event, the investigator will arrange for follow-up visits or telephone calls until the adverse event has resolved or stabilized. Patients who withdraw from the study will not be replaced.

12. Quality Control and Quality Assurance

- 12.1. Quality Control
 - 12.1.1. In Process Quality Control of Biometrics

As per DataClin CRO SOPs, quality control by an independent qualified reviewer is performed on all biometrics related documents developed internally. This includes study protocol, case report form, informed consent form and study plans. In addition to these documents, database QC is performed automatically (programmed edit checks) and manually (manual review of line listings) to ensure that data is complete and consistent.

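### Section 8.3 gives LOCF as the only missing-data rule for week-36 CDAI and HAQ, in a set called intention-to-treat that omits dosed patients without a post-treatment score; the change could be biased either way

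*Combined protocol and SAP*

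**What the plan says.** Section 8.3 (Analysis Population) gives the primary analysis the label intention-to-treat and defines its set as "including all eligible enrolled patients with at least one treatment dose and post first assessment score (CDAI and HAQ) attending any post treatment visit". It then states that "efficacy variables will be analyzed using the last-observation-carried-forward convention (LOCF". Its first sentence places all clinical data on the intention-to-treat basis.

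Sections 8.4.1 and 8.5.1 set both primary endpoints between baseline and week 36. CDAI at those two times is used "to measure disease severity and relative mean change between study endpoints", and HAQ is used for relative change only. Section 8.7.2 plans a "Paired t-test and repeated measure ANOVA test to estimate the change in numerical variables throughout the study visits" but gives no rule for missing values. Section 8.8 says only: "Procedure for accounting for missing, unused, and spurious data will be explained in the statistical analysis plan (SAP". No sensitivity analysis for missing data appears in the supplied text.

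On attrition, section 8.1 and the synopsis size the study at 332 patients "plus an expected drop-out rate of 20% during the 9 months observational study duration", giving 398, rounded to 400. Section 11.5 states: "Patients who withdraw from the study will not be replaced". Sections 10.7 and 11.5 foresee leaving for insufficient response, adverse events and disease progression, and the withdrawal reason is recorded in the CRF. Section 9.2 puts the start of improvement at 4 to 6 weeks, with possible further gain up to 4 to 6 months.

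**The concern.** LOCF gives an unbiased week-36 mean only if leavers' last recorded scores equal, on average, what they would have had at week 36. The protocol's own text gives reasons to doubt this in both directions.

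- **Understatement.** Visits 2 and 3 fall at weeks 6 and 12. Section 9.2 allows improvement beyond those visits, so a score carried from them can miss later gain.
- **Overstatement.** A patient who responds, then loses response and leaves, contributes the better score. The schedule in sections 7.2.1 and 7.2.2 lists six planned visits and no CDAI or HAQ at an early exit. The flowchart in section 6.2 is not shown, so this should be checked.

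Separately, a patient dosed at baseline who leaves before Visit 2 is outside the primary set. That makes it a modified intention-to-treat set, and if early leavers do poorly, omitting them adds to any overstatement.

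There is no control arm in which a similar bias might partly cancel. The size of the change and the share of patients in each CDAI category are what the study will report. One LOCF figure would stand where the missing data leave a range.

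**Working it through.** **The plan's own figures.** Paired noncentral-t power with effect size 0.158, two-sided 5% and 80% power, and n scaled by the signed-rank efficiency 3/π = 0.955, gives n = 332 (power 0.801). This reproduces section 8.1. The inflation is 332 × 1.2 = 398.4, the plan's 398.

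**How many patients are affected.** 20% of 400 is 80. Read instead as the margin over the required number, 400 − 332 = 68.

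**Inputs for the illustration.** The 20% is from section 8.1, and the rough timing of response is guided by section 9.2. All else is assumed:
- mean CDAI of 30, 26, 22, 18, 16.5 and 16 at the six visits;
- leavers spread evenly, one fifth before each of Visits 2 to 6;
- each leaver's last score equal to the completers' mean at that visit.

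Percentages are changes in the mean from 30.

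**80 leavers (16 before each visit).** The 16 who leave before Visit 2 drop out of the set, so n = 384.
- Section 8.3 result: (320×16 + 16×(26 + 22 + 18 + 16.5))/384 = 6440/384 = 16.77, or −44.1%.

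| Leavers' week-36 state | Mean in all 400 | Change | Section 8.3 is off by |
|---|---|---|---|
| Keep improving like completers | 16.0 | −46.7% | 2.6 points understated |
| Lose half their gain (CDAI 23) | (5120 + 80×23)/400 = 17.4 | −42.0% | 2.1 overstated |
| Lose all of it (CDAI 30) | (5120 + 80×30)/400 = 18.8 | −37.3% | 6.8 overstated |

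**68 leavers (13.6 before each visit).** Section 8.3 result: (332×16 + 13.6×82.5)/386.4 = 6434/386.4 = 16.65, or −44.5%. The three reference values are −46.7%, −42.7% and −38.7%, so the errors are about 2.2 under, 1.8 over and 5.8 over.

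**Share due to the set (80 leavers, full loss).** Adding the 16 excluded patients at baseline gives 6920/400 = 17.3, −42.3%, a shift of 1.8 points from −44.1%. Taking the steps in the other order, the reference value in the 384 is 7040/384 = 18.33, −38.9%, against −37.3%, a shift of 1.6. The rest of the 6.8 (5.0 to 5.2 points) comes from LOCF.

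**Sensitivity to timing (80 leavers).** The time course was varied: the base course, a linear ramp from week 4 to month 4, and one from week 6 to month 6. Leavers before Visits 2 to 6 were set at 16 each, 32/24/12/8/4 or 4/8/12/24/32. Over the nine combinations, section 8.3 reports 90.5% to 97.1% of the completers' gain, against a reference of 100%, 90% or 80%. The errors are 1.4 to 4.4 points under, 0.2 to 3.3 over and 4.9 to 8.0 over.

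**CDAI categories.** Assume 5, 12, 21, 26 and 27% in remission or low activity at Visits 2 to 6, with 80 leavers. Section 8.3 gives (320×0.27 + 16×(0.05 + 0.12 + 0.21 + 0.26))/384 = 25.2%. This compares with 27.0% if leavers match completers and 320×0.27/400 = 21.6% if no leaver qualifies.

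**Would a missing-at-random model be better?** In this illustration it returns −46.7% in all three cases, with errors of 0, 4.7 and 9.3 points against 2.6, 2.1 and 6.8. Neither method is uniformly closer.

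**The case against.** The strongest reply is that section 8.8 sends missing-data procedures to a SAP whose content is not in the supplied text, so sensitivity analyses may already be planned. That stands as far as it goes. A reader might infer that the study has no sensitivity analysis at all, and the documents do not support that. But section 8.3 already fixes LOCF and the set, so the two sections must still be aligned, and an imputation rule elsewhere would not correct the set's label.

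The illustration is also open to attack, fairly.
- **The gain is assumed.** With an assumed visit SD of 10 and correlation 0.8 between adjacent visits, a 14-point fall is a standardised effect of about 14/11.6 = 1.21, some 7.6 times the 0.158 in section 8.1. Scaled to 0.158, errors of 2.6 and 6.8 points become about 0.3 and 0.9. However, 0.158 is an effect to be detected, not one expected, and the error relative to the gain is unchanged.
- **The overstatement cases are stylised.** Patients leaving for insufficient response or progression may already have poor recorded scores, which LOCF would carry. That would shrink the overstatement.
- **No estimand is fixed** for patients who stop or change treatment, so the three reference values are scenarios and not a known truth.

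The set's criteria are stated openly, so part of that issue is the label. The synopsis visit table says "Clinical Assessment if applicable", but that table is broken in the supplied text, and the detailed schedule lists CDAI and HAQ at all six visits. This is a point to confirm and not evidence of missing data.

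**Conclusion.** The concern holds, as something that should be fixed. Following section 8.3 as written can bias the week-36 change in either direction, and one LOCF figure would not show which.

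On the assumed inputs, with 68 to 80 leavers, the result is understated by about 2 to 3 percentage points if leavers keep improving. It is overstated by about 2 if they lose half their gain and by about 6 to 7 if they lose all of it. Only the drop-out figure and the approximate timing of response come from the documents. Drop-out timing, reasons, response size and leavers' last scores are assumed.

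Three stronger readings are tempting but not supported. The documents do not show that LOCF will inflate efficacy, since the direction depends on why and when patients leave. They do not suggest that the test against baseline would fail; it would probably not reverse. They also do not say outright that adverse events are counted only in the restricted set. The first sentence of section 8.3 allows that reading, while section 8.4.3 speaks of patients using leflunomide, so the point needs stating.

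**What to change.** Amend section 8.3 and align it with section 8.8.

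1. Define the full analysis set as all eligible patients with at least one dose, or rename the present set modified intention-to-treat.
2. Pre-specify, beside LOCF, a missing-at-random analysis using all six scheduled visits with baseline in the outcome vector (multiple imputation or likelihood-based repeated measures), so that patients with no post-baseline score are kept. State whether mean relative change is the change in means or the mean of individual percent changes, and derive it accordingly. Which analysis is primary is the sponsor's choice.
3. Pre-specify a delta analysis that moves leavers' week-36 CDAI and HAQ 50% and 100% back towards their own baseline. Do this first for all leavers, then only for those leaving for insufficient response, adverse event or progression, using the recorded reason.
4. For CDAI categories, add a sensitivity analysis that counts leavers as not in remission or low activity, declared as a different estimand.
5. State that AE/SAE frequency uses all patients with at least one dose.

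Before finalising, confirm that CDAI and HAQ are collected at every visit, and state whether they are recorded at an exit contact.

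The cost is wording and programming, with no extra patients or visits. The reported range may look less favourable than a single LOCF figure: in the 80-leaver illustration, down to −37.3% beside −44.1%, and 21.6% beside 25.2% in remission or low activity.
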